8.3 Study Calendar

Evaluation and treatment	Screening	Cycle 1 Day 1	Cycle 2 (D22+/-5 days)	Cycle 5 (D64 +/- 5 days)	Cycle 7 and every 2 cycles	Follow up⁹
Time	Baseline (within 6 weeks)	Prior to talimogene laherparepvec injection				
Eligibility, screening, consent, and registration	X					Patients will be monitored for 1 year after removal from the study or until death, whichever occurs first.
Medical history	X					
Staging with tumor measurements	X					
Photography of chest wall	X ¹		X	X	X	
Biopsy of local recurrence [HE, IHC]	X ⁸			X ⁸		
Biopsy of easily accessible distant metastasis [HE, IHC]				X ⁸		
Correlative immune study	X			X ⁷		
Physical examinations, vital signs	X	X ²	X	X	X	
ECOG PS	X	X ²	X	X	X	
Hematology assessment and Biochemical profiles ^{3,5}	X	X ²	X	X	X	
Tumor markers (CA27.29) ¹¹ , IgG (baseline only)	X			X	X ¹¹	
Chest X-ray; Breast sonography ¹³	X					
Pregnancy test if applicable ¹⁰	X					
PET-CT or CT scan of bone/abdomen/chest as clinically indicated	X			X	X ⁴	
Disease assessment ¹²				X	X	

Adverse events ⁵	X	X	X	X	X	
Talimogene Laherparepvec injection ⁶		X	X	X	X	

1. Within 1 week prior to treatment
2. No need to repeat if within 7 days from baseline
3. Hematology include CBC, differential count and platelet count; and biochemical profiles SMA include Na, K, BUN, creatinine, Mg, calcium, AST, ALT, LDH, total bilirubin
4. Repeat every 4 cycles as clinical indicated
5. Before each cycle. Reporting exposure to talimogene laherparepvec and should be collected for the duration of the study and safety f/u
6. Starting cycle 2, Talimogene Laherparepvec injection will be given every 2 weeks until disease progression
7. Correlative immune study will be repeated before cycle 5 and at the end of study if available.
8. Core biopsy of local recurrence at baseline if samples (i.e., paraffin block or 5-10 unstained slides) from the local recurrence are not available. Core biopsy of either distant metastasis or local recurrent lesions before cycle 5 based on patient status.
9. a. Safety Follow-Up: should be conducted approximately 30 days after the last dose of trial treatment or before the initiation of a new anti-cancer treatment, whichever comes first. Safety Follow-Up Visit can be done in the clinic, or by phone if patient is not willing to come to the clinic for follow up.
- b. Unexpected AEs: Patients removed from study for unexpected adverse events will be monitored until AE is resolved or stabilized.
- c. Survival Follow-Up: approximately every 3 months patient survival information will be followed by chart reviewing, or by phone up to 1 year.
10. Female patients of childbearing potential must have a negative urine or blood pregnancy test no more than 3 days prior to starting study drug.
11. Tumor markers (CA 27.29) will be assessed at baseline, before cycle 5 and every additional 4 cycles of treatment. IgG and IgM will be tested at baseline only
12. Disease assessment will be performed at the end of cycle 4, cycle 8 and cycle 10
13. Breast sonography with axillary assessment if clinically indicated

Abbreviation; HE: hematoxilin and eosin staining, IHC: immunohistochemical staining,: talimogene laherparepvec

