6.0. Treatment plan

6.1 Talimogene laherparepvec injection

Talimogene laherparepvec will be given via intra-tumoral injection at visible locally recurrent breast cancer site and skin metastases if indicated at an initial dose of 10^6 PFU/mL for all sample size of 35. If patient has multiple lesions the lesion selection as the following:

- 1) If the largest lesion is > 5 cm, only this lesion will be used for injection;
- 2) If the largest lesion is < 5.0 cm, we will prioritize the size of the lesions (from large to small), and administer talimogene laherparepvec based on injection guideline in Table 3 below. The maximum dose of each course should not exceed 4.0 mL.
- 3) If patients do not have distant metastases, the lesion of lowest priority for injection should be left uninjected at least until it is biopsied.

The injection dose will not be affected by patients' actual body weight. The second talimogene laherparepvec dose will be administered 10^8 PFU/mL on day 22, and talimogene laherparepvec will be administered every 2 weeks after the second course with same dose with the maximum dose of 4.0 mL for each course (Figure 4). The injection dose varies according to the tumor spread area and using the talimogene laherparepvec injection volume guideline based on tumor size (Table 3). Distribution of the injection to separate sites will be permitted if the lesion is more than 5.0 cm diameter and/or multiple lesions. When disease diameter is greater than 5.0 cm and difficult to inject uniformly, we divide disease location tetrameric injection site with 1.0 mL administration each. On each treatment day, injections should be prioritized as follows:

[figure not shown]
- any new injectable tumor that has appeared since the previous injection
- by tumor size, beginning with the largest tumor and then the second largest tumor if agent available, otherwise treat in the following courses
- by tumor size, when similar size tumor exist, prioritize one and then the other tumor if agent available, otherwise treat in the following courses
- by tumor size, when huge tumor exist (greater than 10.0 cm), inject talimogene laherparepvec at different site for aiming uniform distribution in the following course.
- any previously uninjectable tumor(s) that is now injectable

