6.4 Permanent Discontinuation of Treatment and Withdrawal of patients from study

Talimogene laherparepvec is to be permanently discontinued for patients meeting any of the following criteria:

- The patient, for any reason, requires treatment with another anticancer therapeutic agent for the study disease (other than the exceptions noted in the protocol, if applicable). In this case, discontinuation from the treatment occurs immediately upon the introduction of the new agent.
- Confirmed PDA grade 2 or greater Immune-mediated adverse events (with the exception of vitiligo) or allergic reactions attributed to talimogene laherparepvec that would require a dose delay of greater than 6 weeks from the date of the planned dose (i.e., approximately 8 weeks from the previous dose).
 - Note: immune-mediated glomerulonephritis, vasculitis, and pneumonitis and exacerbation of psoriasis have been observed in subjects receiving talimogene laherparepvec in clinical trials. Most of these subjects had a history of other autoimmune disease and/or prior treatment with agents that offered plausible alternative etiologies, however, immune-mediated adverse events can potentially involve any organ system.
- Any other talimogene laherparepvec-related non-hematologic or hematologic toxicities grade 3 or greater occur that, in the opinion of the investigator, would require a dose delay of greater than 4 weeks from the date of the planned dose (i.e., approximately 6 weeks from the previous dose).
- The subject develops clinical evidence of any systemic herpes infection (such as encephalitis or disseminated infection).
- A female subject becomes pregnant or fails to use acceptable method(s) of effective contraception (for those subjects who are able to conceive).
- A female subject breast feeds while on study treatment.
- Concurrent medical illness that, in the judgment of the investigator, would make continued treatment with talimogene laherparepvec dangerous for the subject.
- For additional information related special warnings and precautions for the use of talimogene laherparepvec please refer to the latest version of the Talimogene Laherparepvec Investigator's Brochure.
- Dosing noncompliance: If dosing compliance is not 100% (administration of talimogene laherparepvec on the scheduled date +/- 3 days in the absence of toxicity), the study treatment should be discontinued for the patient.
- Complete remission of locally recurrent disease with or without distant disease

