6.5 The end of study

6.5.1. Definition of the end of the study

Previous talimogene laherparepvec single agent study showed that the median time to response was 4.1 months, and 50 % of these responders had progressive disease (PD) (defined by modified WHO criteria) prior to response. In this study talimogene laherparepvec administration will continue for at least 10 cycles (approximately 5 months) unless uncontrolled disease progression is observed. Beyond 10 cycles, progressive disease will be measured based on RECIST ver1.1.

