6.5.2. Uncontrolled disease progression

Uncontrolled disease progression is defined as rapid growth of multiple measurable or non-measurable new lesions, or sum of the longest diameter of existing targeted lesions is >40% from the baseline.

Immunotherapeutic agents such as talimogene laherparepvec may produce antitumor effects by potentiating endogenous cancer-specific immune responses. The response patterns seen with such an approach may extend beyond the typical time course of responses seen with cytotoxic agents, and can manifest a clinical response after an initial increase in tumor burden or even the appearance of new lesions

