8.0. Evaluation during study

The window for all assessments and treatments should be completed within 5 days of the scheduled time.

Patients will be allowed to continue current hormonal therapy, selected chemotherapy, targeted agents and/or anti-HER-2 therapy, which will be administered as standard of care, (per physician discretion) while receiving study drug.

8.1. Evaluation during talimogene laherparepvec:

- 8.1.1. Patients will have a CBC, differential count and platelet count before each cycle.
- 8.1.2. Patients may repeat the CBC, differential count and platelet count until recovery of these measures before the next cycle (absolute neutrophil counts \geq 1,000 and platelets \geq 100,000 per mm³).
- 8.1.3. Medical history and physical examination with vital signs, weight, and PS before cycles 2 and 5 and every additional 2 cycles of treatments.
- 8.1.4. Digital photography of chest lesions before cycles 2, 5, and every additional 2 cycles of treatment.
- 8.1.5. Toxic effects will be assessed before each cycle.
- 8.1.6. SMA (Na, K, BUN, creatinine, Mg, calcium, AST, ALT, glucose, LDH, and total bilirubin) will be performed before each cycle.
- 8.1.7. Levels of tumor markers (e.g., cancer antigen CA 27.29) will be assessed before cycle 5 and every additional 4 cycles of treatment.
- 8.1.8. Systemic immunity in serum or plasma levels of GM-CSF, IL-2, IL-12, TNF-alpha (α), IFN- alpha (α); and phenotype for T-cell subsets (CD3, CD4, CD8, CD25), and NK-cell subsets (CD16, CD56) will be determined via multiparameter FACS analysis (percentage and absolute numbers) before cycle 5 and at the end of study in [name] laboratory at MD Anderson.
- 8.1.9. PET-CT or CT of bone/ abdomen/chest should be performed before cycle 5 and before every additional 4 cycles of treatment as clinically indicated.
- 8.1.10. Disease assessment will be done at the end of cycle 4, cycle 8 and cycle 10.

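### Calendar footnote 6 stops injections at any disease progression, while sections 6.5.1 and 6.5.2 keep dosing to at least cycle 10 unless progression is uncontrolled

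*Combined protocol and SAP*

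**What the plan says.** Two parts of the protocol tell the site how long to inject.

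- **Study Calendar (8.3), footnote 6:** "Talimogene Laherparepvec injection will be given every 2 weeks until disease progression". It does not say confirmed, true or uncontrolled progression, and it does not refer to 6.5 or 9.4.
- **Section 6.5.1:** "talimogene laherparepvec administration will continue for at least 10 cycles (approximately 5 months) unless uncontrolled disease progression is observed", followed by "Beyond 10 cycles, progressive disease will be measured based on RECIST ver1.1".
- **Section 6.5.2** defines the exception: several new lesions growing rapidly, or "sum of the longest diameter of existing targeted lesions is >40% from the baseline".

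Section 9.4 gives the ordinary definition of PD: a target sum at least 20% and 5 mm above the smallest on study, or one or more new lesions. It then says that, for this study, true PD is settled at the end of cycle 10. Assessment times are in 8.1.10: "Disease assessment will be done at the end of cycle 4, cycle 8 and cycle 10".

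**The concern.** A calendar is what staff use on the day of a visit. The Cycle 5 column carries both the first disease assessment and an injection governed by footnote 6, so the two rules meet when someone must decide whether to inject.

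The protocol deliberately treats through early growth. Sections 6.5.1 and 9.4 cite the earlier melanoma experience, in which about half of responders progressed before responding and the median time to response was 4.1 months. Section 9.5 builds this into the primary endpoint: early PD that is not confirmed at the end of cycle 10 does not rule out an overall response. A site that follows the footnote takes such a patient off drug before that confirmation, after fewer injections than 6.5.1 intends.

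**Working it through.** **1. Schedule.** Inputs from 6.1: cycle 1 on day 1, cycle 2 on day 22, then "talimogene laherparepvec will be administered every 2 weeks after the second course". For cycle k from 2 onward, the injection day is 22 + 14 × (k − 2).

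Check against the plan's own figures:
- Cycle 5: 22 + 14 × 3 = day 64, as in the calendar.
- Cycle 10: 22 + 14 × 8 = day 134, ending on day 134 + 14 = 148. That is 147 days after day 1, or 147 / 30.44 = 4.8 months, in line with the stated 5 months or so.

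Also needed: cycle 4 on day 22 + 28 = 50, and cycle 8 on day 22 + 84 = 106.

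**2. What each rule instructs at the end of cycle 4 or cycle 8.**

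| Finding | Footnote 6, read with 9.4 | 6.5.1 with 6.5.2 |
|---|---|---|
| No PD | continue | continue |
| Target sum up 25% and at least 5 mm, no earlier shrinkage | stop | continue |
| One new lesion | stop | continue |
| Target sum up more than 40% from baseline and at least 5 mm | stop | stop |

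The middle two rows conflict. Beyond cycle 10, 6.5.1 applies RECIST 1.1 PD and the texts agree.

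**3. Width of the band for target lesions.** Assume no earlier shrinkage, so the smallest sum is the baseline sum B, and read the 6.5.2 limit as an increase of more than 40%. The footnote stops at max(1.2 × B, B + 5); 6.5.2 stops only above 1.4 × B.

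- B = 50 mm: max(60, 55) = 60 mm, against 70 mm. The rules differ from 60 to 70 mm.
- B = 20 mm: max(24, 25) = 25 mm, against 28 mm. The rules differ from 25 to 28 mm.

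Where the sum has first shrunk, the 9.4 threshold moves down with it while the 6.5.2 limit stays tied to baseline, so the band is wider.

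**4. Exposure lost per affected patient.**

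- Stop at the end of cycle 4: 10 − 4 = 6 of the 10 minimum injections omitted. The last injection is on day 50, which is 148 − 50 = 98 days before the end of cycle 10.
- Stop at the end of cycle 8: 10 − 8 = 2 of 10 omitted. The last injection is on day 106, which is 148 − 106 = 42 days before.

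**5. Which rule was intended.** The rest of the protocol sides with 6.5.1:

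- Section 6.1 puts first in the injection order "any new injectable tumor that has appeared since the previous injection", although any new lesion is PD under 9.4.
- Section 9.4 defers true PD to the end of cycle 10, provided treatment is tolerated.
- Sections 9.5 and 9.6 let response and disease control stand when early PD is not confirmed then.
- The PFS example in 13.1 has a patient progressing at 2 months and in partial response at 5 months.

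**The case against.** The best defence is that footnote 6 was never meant as a complete stopping rule. Its main job is the two-week interval. It also leaves out complete remission, toxicity, pregnancy and withdrawal of consent, and nobody would take it to cancel those. Uncontrolled progression is itself a kind of progression, so the line could be shorthand for progression as 6.5 handles it, and a site with a stopping question has a section on exactly that.

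Part of this stands. The intended rule can be recovered, and no effect on the trial as a whole has been shown. But the footnote is not merely silent: it names a stopping event, and 9.4 attaches to that term a lower threshold than 6.5.2. Reading it as true PD at cycle 10 would lose the early stop for uncontrolled progression. Reading it as 6.5 in brief requires a cross-reference that is not there.

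A reader might also infer three stronger things that the documents do not support.

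- **A loss of power.** It is tempting to carry over the melanoma figure of about 50%. That figure comes from another disease under modified WHO criteria, and nothing in the protocol says what share of responses would be lost if dosing stopped at first PD.
- **A missing, or a safe, cycle 10 assessment.** Section 8.1.10 sits under evaluation during treatment, and the calendar's numbered follow-up items cover safety, unexpected adverse events and survival. The footnote does not cancel the assessment, but neither does any text establish that a patient who has stopped injections would still have it.
- **Section 6.4 omits progression, so progression is no reason to stop.** The second item in that list opens with what looks like a separate entry for confirmed PD run into an immune-event entry. If so, 6.4 does name progression, in a qualified form that footnote 6 lacks.

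**Conclusion.** Wrong as written, and it should be fixed. Up to cycle 10, footnote 6 and section 6.5 give opposite dosing instructions for a patient whose PD under 9.4 falls short of uncontrolled progression. Patients without early PD, and those who would stop under 6.5.2 anyway, are unaffected.

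The cost is 6 of 10 minimum injections per affected patient for a stop at the end of cycle 4, or 2 of 10 at the end of cycle 8. This assumes that the site follows the footnote literally, that doses are given on schedule, and that cycle 1 counts toward the 10. The number of such patients, and the effect on the response rate, cannot be derived from the documents.

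**What to change.** Reword footnote 6 along these lines:

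> Cycle 2 is given on day 22 and later cycles every 2 weeks, through at least cycle 10 unless uncontrolled disease progression (6.5.2) or a withholding or discontinuation criterion in 6.3 or 6.4 applies; early PD per 9.4 that is not uncontrolled does not by itself stop dosing before the end of cycle 10; beyond cycle 10, until PD per RECIST 1.1 (see 6.3 to 6.5).

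The reference to 6.3 is needed because 6.3.1 (ongoing antiviral treatment) and 6.3.3 (related adverse event delaying a dose by more than 6 weeks) contain discontinuation rules that 6.4 does not fully repeat.

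The cost is one footnote. The visits, the sample size, the two-stage rule (0 of 13, then 3 or fewer of 35) and its stated 8.4% and 90% do not change, since none of them depends on this line.

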1.3 Correlative studies

- To determine the effect of talimogene laherparepvec on injection sites and distant metastatic sites by evaluating immune function and apoptosis with immune cell surface markers and cytokines. Talimogene laherparepvec induces systemic immune reaction through activation of dendritic cell, and enhance cellular immunity. Cytotoxic T-lymphocyte (CTL) is estimated to offense distant cancer cells via apoptosis mechanism and humoral immunity was not determined to involve in this systemic immunity. However, the activation of dendritic cells may subsequently activate NK-cells and B-cells. Other leukocyte such as neutrophil and monocyte are currently undetermined their function within systemic immune reaction induced by talimogene laherparepvec (Figure 1).
- To assess changes in the following:
 - Serum or plasma levels of interleukin (IL)-2, IL-12, tumor necrosis factor (TNF)-alpha (α), and interferon (IFN)-alpha (α); ([name]'s Lab)
 - Phenotype for T-cell subsets (CD3, CD4, CD8, CD25) and NK-cell subsets (CD16, CD56), which will be determined via multiparameter FACS analysis (percentage and absolute numbers) in peripheral blood at [name] laboratory of MD Anderson.
 - Serum analysis of herpes simplex virus (HSV) type 1 serology with immunoglobulin (Ig)G and IgM (ELISA)
- To assess distant tumor tissue changes by evaluating necrosis and immune cell infiltration (T-/B-/NK-Cell, macrophage, dendritic cell) by immunohistochemistry assay (CD3, CD4, CD8, CD20, CD16, CD56, Granzyme B, cleaved caspase 3, and Ki-67) when distant tumor sample is obtained. If the sample volume is ample, additional immunohistochemistry assays will be performed for CD45RO, TIA-1, FoxP3, CD25, OX-

40, CD57, CD1a, CD208, myeloperoxidase, CD68, COX-2, MHC Class I and MHC Class II in [name] laboratory at MD Anderson.

Figure 1: Systemic immune response expected to be related to talimogene laherparepvec administration

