7.2.12. Breast sonography with axillary assessment if clinically indicated

7.2.13. Ultrasound-guided core biopsy of local recurrence if samples (i.e., paraffin block or 5-10 unstained slides from the local recurrence) are not available. The imaging physician will perform the biopsy if indicated at MD Anderson.

7.2.14. HSV serology: serum HSV type 1 IgG.

7.2.15. Systemic immunity in serum or plasma levels of, IL-2, IL-12, TNF-alpha (α), IFN- alpha (α); and phenotype for T-cell subsets (CD3, CD4, CD8, CD25), and natural killer-cell subsets (CD16, CD56) will be determined via multiparameter fluorescence activated cell sorting (FACS) analysis (percentage and absolute numbers) in [name] laboratory at MD Anderson.

7.2.16. Photography of the local recurrence in the chest wall.

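### Change in HSV-1 IgG and IgM is a correlative objective, but serology is scheduled at baseline only; separately, GM-CSF is in the on-treatment panel and not in the baseline panel

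*Combined protocol and SAP*

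**What the plan says.** All references are to the combined protocol and SAP.

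**The objective.** Section 1.3 introduces a list with "To assess changes in the following". The list has three items: a set of cytokines ("Serum or plasma levels of interleukin (IL)-2, IL-12, tumor necrosis factor (TNF)-alpha", then IFN-alpha), T-cell and NK-cell subsets, and HSV-1 serology covering both IgG and IgM by ELISA. GM-CSF is not in the list.

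**The serology schedule.**
- Section 7.2.14, pretreatment: "HSV serology: serum HSV type 1 IgG". IgM is not mentioned.
- Section 8.3, the calendar row shared with CA 27.29: "IgG (baseline only" in brackets. Again there is no IgM.
- Section 8.3, footnote 11: "IgG and IgM will be tested at baseline only".
- Section 8.1, evaluation during treatment: no serology item.

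**The cytokine schedule.** The pretreatment panel in 7.2.15 reads "Systemic immunity in serum or plasma levels of, IL-2, IL-12, TNF-alpha" and continues with IFN-alpha and the cell subsets. The on-treatment panel in 8.1.8 reads "Systemic immunity in serum or plasma levels of GM-CSF, IL-2, IL-12, TNF-alpha" and continues in the same way. It is drawn before cycle 5 and at end of study. The calendar marks a correlative immune study at screening and at cycle 5. Footnote 7 says it is repeated, with the end-of-study sample taken if available, and names no analytes.

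**The analysis.** Section 13.1 says biomarkers are measured before and after treatment, that mixed models will describe their change over time, and that change in markers will be related to response.

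**The concern.** A change needs at least two values per patient, one of them before treatment if it is to be a change from baseline. The serology schedule supplies one time point and the objective needs two. The listed GM-CSF schedule supplies only later values, while section 13.1 describes biomarkers in general as measured before and after treatment.

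Both measures bear on the proposed mechanism. The agent is a modified HSV-1 that carries the GM-CSF gene. The note to Figure 4 links the first-course dose to possible seronegativity, and section 4.4.2 says earlier studies sampled before and after dosing to assess serostatus. Section 4.4.3 also acknowledges, for T cells in phase 1 biopsies, that without baseline data no treatment-related rise could be concluded. A post-treatment GM-CSF level with no pretreatment level has the same limitation.

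At stake is one stated correlative objective (serology), and the before-and-after reading of one marker (GM-CSF).

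**Working it through.** No sample size, power or error-rate figure bears on this point, so the check is a count of scheduled time points for each analyte.

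**Rule.** Change from baseline is computable if there is at least one baseline value and at least one later value. Change between later draws is computable if there are at least two later values.

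**Inputs.** Baseline: 7.2.14, 7.2.15, the calendar row and footnote 11. Later: 8.1.8, footnote 7 and footnote 11. Planned enrolment: up to 36 (section 5.0).

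| Analyte | Named in the 1.3 change list | Baseline values | Later values | Change from baseline | Change between later draws |
|---|---|---|---|---|---|
| HSV-1 IgG | yes | 1 | 0 | no | no |
| HSV-1 IgM | yes | 1 by footnote 11; 0 by 7.2.14 and the calendar row | 0 | no | no |
| IL-2, IL-12, TNF-alpha, IFN-alpha | yes | 1 | up to 2 | yes | yes, if both drawn |
| T-cell and NK-cell subsets | yes | 1 | up to 2 | yes | yes, if both drawn |
| GM-CSF | no | 0 by 7.2.15 | up to 2 | no | yes, if both drawn |

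**Can another passage supply the missing serology?**
- The shared calendar row has marks at cycle 5 and later. These belong to CA 27.29, because the bracket restricts IgG to baseline.
- Footnote 7 repeats the correlative immune study without listing its contents. Footnote 11 deals with serology by name and restricts it to baseline. The specific statement governs.

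So 0 of up to 36 patients would have a computable change in IgG or IgM under the written schedule.

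**Can another passage supply the baseline GM-CSF?** Possibly. The calendar marks the immune study at screening, and the word repeated suggests the same panel each time. However, 7.2.15 is the only baseline analyte list, and it omits GM-CSF.

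**Patients already treated.** Section 13.1 records 8 patients treated at the time of one revision. Had 7.2.15 been followed for them, at most 36 − 8 = 28 could still have a baseline GM-CSF taken prospectively. More may have been treated since, so 28 is an upper limit.

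**The case against.** **Serology.** Baseline-only testing is stated twice in 8.3, which looks deliberate, and the documents do give baseline serostatus a role (the note to Figure 4; the seronegative patients in 4.4.3). The wording of 1.3 may therefore be the error, and the schedule correct. This stands as an argument about which text to change. It does not remove the contradiction, because 1.3 still promises a change that cannot be measured.

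**GM-CSF.** Three points stand.
- Section 1.3 does not name GM-CSF. A reader might infer that a stated objective fails for it, as it does for serology. The documents do not support that: the need for a baseline comes only from the general biomarker text in 13.1.
- A reader might also infer that no change in GM-CSF can be computed for anyone. That goes too far. Section 8.1.8 schedules two values, so a difference between them is available for patients with both. Only change from baseline is lost.
- Baseline GM-CSF may have been intended. The stray comma in 7.2.15 sits where 8.1.8 names GM-CSF. It could mean that GM-CSF was deleted there on purpose and left behind in 8.1.8, that it was lost by accident, or simply that the text was converted badly. The documents do not settle this.

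**Feasibility.** The panels are described as serum or plasma, while 1.3 calls for serum for the HSV ELISA. No blood volumes are given and no banking of baseline serum is described. It cannot be taken as given that existing samples would serve.

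**Importance.** Neither measure appears in 13.2 or 13.3, and no trial decision depends on either. That limits the weight of the point but does not answer it.

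**Conclusion.** The serology point holds in full. Change in HSV-1 IgG and IgM is a stated correlative objective, every scheduling passage gives baseline testing at most, and 0 of up to 36 patients could contribute a change. The omission of IgM from 7.2.14 and the calendar row is a further inconsistency.

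The GM-CSF point holds in a narrower form. The baseline and on-treatment panels do not match, and change from baseline cannot be computed from the panels as listed, contrary to the before-and-after analysis in 13.1. This assumes that 7.2.15 is the complete baseline panel.

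The consequence is confined to correlative analyses. The text should be corrected, but nothing here touches the primary endpoint, the two-stage design or the toxicity monitoring.

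**What to change.** **Serology.** Amend footnote 11 and the calendar row so that HSV-1 IgG and IgM are also run at the correlative draw before cycle 5, and at end of study when a sample is available. Add IgM to 7.2.14 and to the calendar row. The pre-cycle-5 draw should be the main post-baseline point, since the end-of-study sample is conditional. If serology is wanted only as a baseline characteristic, move it out of the list of changes in 1.3 instead.

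**GM-CSF.** Reconcile 7.2.15 with 8.1.8. Either add GM-CSF to the baseline panel for patients still to be enrolled, using stored pretreatment samples for earlier patients if any exist, or state in 13.1 that GM-CSF is excluded from change-from-baseline analyses.

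**Cost.** A protocol amendment and a small assay expense, with no new visit. The added serology assumes a serum aliquot of sufficient volume at the existing draws, which the site laboratory should confirm. Rewording 1.3 and 13.1 costs only the amendment, but it gives up the change in serology and the GM-CSF change from baseline. A baseline GM-CSF value not taken before treatment cannot be recovered later without stored samples, so this should be settled before further enrolment.
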